10.5 Timing of assessments/trial visits

All trial visits can be scheduled to coincide with routine clinical appointments and can be in person or remote, depending on the participant's preference. Ideally, the baseline visit and visit at 12 months will be in person but can be arranged via alternative approaches if participant preference and if needed due to the pandemic situation, or if routine clinical appointments are generally not being conducted in person. Any tests that are not possible to be performed as part of the visit (i.e. blood test) can be organised via the routine clinical pathway. Recruitment of participants who may have limited mobility or who live some distance from the study site, can be carried out during a home visit if the local trial team are able to provide home visits. Remote visits may mean a telephone consultation or using video technology if this is used in routine clinical appointments. Participants can also use email and post in addition to telephone communication with the trial team if needed for different reasons.

After obtaining informed consent, the following visits/follow-ups for trial participants are planned. The trial follow-up period will be a variable duration depending when the participant is recruited to the trial. It is anticipated for the trial cohort as a whole, to have a likely median follow-up of 24 months. However, this is dependent on guidance during the trial from the TSC. A common end date of the trial will be set during the trial, several months in advance to facilitate end of trial follow-up.

- Baseline/recruitment visit
- **1 week (+/-7 days):** telephone call to check received trial medications.
- 3 months (+/-14 days): telephone call follow-up
- 6 months (+/-14 days): telephone call follow-up
- **12 months (+/-14 days):** in person follow-up/remote can be arranged if needed
- Then every 6 months approximately (telephone or in person alternate) (+/-14 days) until end of trial
- After participant's scheduled follow-up has completed: Hospital episode statistics and ONS data (for mortality) will

Hospital episode statistics and ONS data (for mortality) will be collected for participants over the OPACE trial period until the specified common end date of the trial, if available. These data will be analysed for clinically important outcomes, i.e. hospital admissions and mortality.

• Additional follow-up if needed: If a participant has any medical concerns or issues related to participating in the trial, they can raise these with the trial team who will arrange a further follow-up with the trial team if indicated, or advise to seek help via their GP/specialist/emergency medical help if appropriate.

An approximate +/- 14 days window for each follow-up visit and telephone follow-up is permitted. These are provided as an approximate window for conduct of follow-ups. It is recognised that for various reasons it may be difficult to schedule within these specific time windows. If so, follow-up should be scheduled as close to the time window as possible.

In the event that a participant is unable to attend a scheduled assessment visit because of an acute illness e.g. exacerbation of COPD, or other reason, the visit will be appropriately postponed, ideally within 6 weeks of scheduled assessments. However, it is recognised for different reasons this may be longer.

10.5.1 Baseline visit (visit 1)

Following obtaining informed consent, data will be collected for the following information required to answer the trial objectives.

Participants in their baseline visit will also be given/sent out in the post a trial card with relevant information on it, which is important for them to present to healthcare providers to let them know of their participation in the trial if needed.

Further information regarding exacerbations management is provided in section 8.8 and will be highlighted to participants at baseline and in trial information. The process of participant notification of exacerbations will be detailed in the TPM. As per section 10.4.3, participants will be provided with a trial diary card to record exacerbations and advised how locally to notify the trial team to let them know if they have had an exacerbation(s) during the trial.

The Participant Information Sheet and the Participant ID trial card will provide participants information on how they can contact the trial team if they have any concerns regarding their trial participation, trial medication or exacerbations.

Data collection from healthcare records and/or participant reported that will be recorded at baseline visit are stated in Section 10.4.5.

Assessments performed to include:

- Height
- Weight
- BMI
- Exacerbation history, medical history
- Questionnaires:
 - Disease related health status (COPD Assessment Tool (CAT), chronic bronchitis, cough visual analogue score (VAS))
 - General health (anxiety-GAD-2, depression-PHQ-2, frailty-SHS)
 - Health related quality of life (EQ-5D-5L)
- Adverse events (AEs) and serious adverse events (SAEs). Please see section 11.3.
- Spirometry (unless there is a result available from within the previous 2 years). FEV₁/FVC will be recorded.
- Blood test-FBC (unless there is a result available from the last 6 months)
- SWAP: (evaluation of SHS and CFS, data recorded to enable calculation of eFI and Cambridge multimorbidity score)

10.5.2 Week 1 (+ 14 /- 7 days) telephone call

- Confirm participant is content to continue to participate in the trial.
- To check received trial medication, understands how to take it and date when started trial medication and check trial medication compliance.
- Assessment of AEs and SAEs. Please see sections 11.4 and 11.5.
- 10.5.3 Telephone follow-up (3, 6 months (+/- 14 days))
- Confirm participant is content to continue to participate in the trial.
- Record any exacerbations details/confirmations; if information regarding exacerbations has already been provided. Healthcare usage.
- Questionnaires
 - CAT score
 - Cough VAS (6 months only)
- Check trial medication compliance-if still on trial medication
- Assessment of adverse events and SAEs. Please see sections 11.4 and 11.5

10.5.4 Visits follow-up (12 months (+/- 14 days), and ~6 monthly (alternate visit or telephone) until end of trial)

- Confirm participant is content to continue to participate in the trial.
- Check smoking status (every 12 months)
- Record any exacerbations details/confirmations; if information regarding exacerbations has already been provided. Healthcare usage.
- Questionnaires
 - CAT score, (every 6 months)
 - Cough VAS, EQ-5D-5L (every 12 months)
- Check trial medication compliance if still on trial medication
- Assessment of adverse events and SAEs. Please see sections 11.4 and 11.5
- SWAP end of trial: SHS, CFS, data to enable calculation of eFI and Cambridge multimorbidity score

10.6 Schedule of Assessments

		Baseline	Trial follow-up, anticipated approximately median 24 months					
Visit		1*	Telephone call•	Telephone follow-up*	Telephone follow-up*	2*	Follow- up** /end of trial	
	Screening	Day 1	1 week	3 months	6 months	12 months	~6 monthly	
Pre-consent screening and approach	Х	Х						
Informed consent		Х						
Baseline assessments (Eligibility confirmation)		Х						
Demographics		Х						
Smoking history		Х						
Smoking status Medical history including cardiovascular disease history		X X				X	X	
Baseline exacerbations history over last 12 months		Х						
Azithromycin duration of use & current prescription		Х						
Concomitant medications		Х						
Healthcare usage				Х	Х	Х	Х	
Height & weight if not done within last 2 years^		Х						
Spirometry^^		Х						
Blood test (FBC)°		Х						
Health records access (lab eosinophils, CT chest, sputum, spirometry reports) if available		Х						
Questionnaires (CAT) score		Х		Х	Х	Х	X	
(CAT) SCOLE		^		^	^	^	^	

TPL001 V10 Authorised 30/05/2022 Reviewed 30/05/2022

EQ-5D-5L	Х				Х	Х		
Cough VAS	Х				Х	Х		
score								
Chronic	Х							
bronchitis								
GAD-2	Х							
PHQ-2	Х							
SHS [⊗]	Х					Х		
CFS [⊗]						Х		
eFI [⊗]						Х		
CMMS [⊗]						Х		
Randomisation	Х							
Adherence		Х	Х	Х	Х	Х		
Adverse event assessments	Х	Х	Х	Х	Х	Х		
Exacerbations		Х	Х	Х	Х	Х		
report during the trial◊		Exacerbation notification throughout trial follow-up. Decision whether to stop trial IMP will need to be made (i.e. if 3 or more exacerbations/year).						
IMP home delivery#	Х			X	X	Х		
Sputum results		if sent						

*can be in person or via remote communication means if needed. (A separate consent consultation in person or remotely prior to Day 1 can be arranged if necessary)

**can be via telephone or other communication means if needed. Given variable duration of follow-up for the trial cohort, not all participants will have the same number of visits/follow-up. The common end date of the trial will be set several months in advance. This will allow sufficient time for an end of trial visit to be arranged within approximately 6 months of the trial common end date for all participants recruited. Participants recruited early in the trial, will have a higher number of follow-ups until end of trial, compared with participants recruited late in the trial, since these participants are recruited closer to the common end date of the trial.

^Height and Weight: if not able to do height and/or weight assessment during visit, reported height and/or weight can be recorded if a remote consultation and/or unable to do during the visit. Height and/or weight measurements can be done at a subsequent trial follow-up/clinical follow-up if not able to perform currently, but maybe able to at a later time.

^^Spirometry. Spirometry performed if participant able to, pending clinical service capacity to provide this and impact of COVID-19 pandemic situation at the time of the trial. Have allowed ~1month from baseline assessment and will not preclude randomisation or start of trial medication. If done in last 2 years approximately can use.

Exacerbations report during the trial. Participants will be advised how to do this depending on local practice and record in participant diary card.

°can be used if done clinically in last 6 months

#currently planned for 6 months delivery, delivery schedule may change.

 $^{\otimes}$ part of study within a project (see Appendix B).

OPACE

10.7 Long-Term Follow-up Assessments

After the active treatment phase of the trial has completed, participants' long term (survival data and hospitalisations) data will be collated until trial end date. This will be via NHS Digital and ONS analogous services in devolved administrations.

10.8 End of Trial Participation

Participants will have finished their active trial participation when they complete their end of trial visit. Participants will return to standard of care following their participation in the trial.

10.9 Trial Restrictions

Trial restrictions in terms of interactions with other therapies are described in section 9.1.1.9.

Pregnancy

Section 4.6 of the SmPC states that azithromycin should only be used during pregnancy if the benefit outweighs the risk.

11 ASSESSMENT OF SAFETY

OPACE trial is a Type B study. Azithromycin is a licensed medication and is recommended as the chemoprophylaxis of choice in guidelines (NICE, GOLD, BTS) for reducing the risk of COPD exacerbations. The dose and frequency used in this trial is as per routine clinical care prescribing.

11.1 Definitions

11.1.1 Adverse event (AE)

Any untoward medical occurrence in a participant or clinical trial participant administered a medicinal product and which does not necessarily have a causal relationship with this treatment.

An adverse event can therefore be any unfavourable and unintended sign (including an abnormal laboratory finding), symptom, or disease temporally associated with the use of an investigational medicinal product, whether or not considered related to the investigational medicinal product.

Please note: Recording of all adverse events must start from the point of Informed Consent regardless of whether a participant has yet received a medicinal product. AEs will be recorded in participant's medical notes.

11.1.2 Adverse reaction to an investigational medicinal product (AR)

All untoward and unintended responses to an investigational medicinal product related to any dose administered. All adverse events judged by either the reporting investigator or The Sponsor as having a reasonable causal relationship to a medicinal product qualify as adverse reactions. The expression reasonable causal relationship means to convey in general that there is evidence or argument to suggest a causal relationship.

11.1.3 Unexpected adverse reaction

An adverse reaction, the nature, or severity of which is not consistent with the applicable reference safety information (RSI). When the outcome of the adverse reaction is not consistent with the applicable RSI, this adverse reaction should be considered as unexpected.

The term "severe" is often used to describe the intensity (severity) of a specific event. This is not the same as "serious," which is based on participant/event outcome or action criteria.

11.1.4 Serious adverse event or serious adverse reaction (SAE / SAR)

Any untoward medical occurrence that at any dose:

- results in death
- is life-threatening
- requires hospitalisation or prolongation of existing inpatient hospitalisation
- results in persistent or significant disability or incapacity
- is a congenital anomaly or birth defect
- is an important medical event Some medical events may jeopardise the participant or may require an intervention to prevent one of the above characteristics/ consequences. Such events (hereinafter referred to as 'important medical events') should also be considered as 'serious'.

Life-threatening in the definition of a serious adverse event or serious adverse reaction refers to an event in which the participant was at risk of death at the time of event; it does not refer to an event which hypothetically might have caused death if it were more severe.

11.1.4.1 Operational definitions for (S)AEs

In this trial

- SAEs will be reported from the time a participant consents to join the trial until the end of trial, if a participant remains on trial medication. Participants who withdraw from taking trial medication will have SAEs reported from the time the participant consents to join the trial until 28 days after ceasing trial medication. Participants who never start taking the trial medication will have SAEs reported for 28 days from the time they consent to join the trial.
- All adverse events and adverse reactions will be recorded for the same period of time described above.
- Hospitalisations for treatment planned prior to randomisation and hospitalisation for elective treatment of a pre-existing condition will **not** be considered, recorded or reported as an SAE.
- Complications occurring during such hospitalisation will also not be considered, recorded or reported as an SAE unless there is a possibility that the complication arose because of the trial medication (i.e. a possible adverse reaction).
- Exacerbations of COPD, pneumonia or hospital admissions as a consequence of exacerbations of COPD or pneumonia will **not** be considered or reported as AEs or SAEs because they are primary and secondary outcomes for the trial. These will be recorded as part of the trial outcomes.

All other SAEs (including SARs) should be reported to the lead site trial office (see front cover of the protocol and SAE Form for SAE reporting contact information).

11.1.5 Suspected Unexpected Serious Adverse Reaction (SUSAR)

A serious adverse reaction, the nature and severity of which is not consistent with the information set out in the Reference Safety Information.

11.1.6 Reference Safety Information (RSI)

A list of medical events that defines which reactions are expected for the IMP within a given trial and thus determining which Serious Adverse Reactions (SARs) require expedited reporting.

The RSI is contained in a clearly identified section of the Summary of Product Characteristics (SmPC) or the Investigator's Brochure (IB).

For this trial, the Reference Safety Information is:

Section 4.8 of the SmPC of Azithromycin 250mg film coated Tablets (Accord-UK Ltd) approved by the MHRA for use in this trial.

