7.8 Trial Outcome Measures

7.8.1 Primary outcome measure

Time to first COPD exacerbation.

7.8.2 Secondary outcome measures

Data pertaining to secondary outcomes will be collected over the entire trial follow-up (i.e. inclusive of time on IMP and if needed off IMP):

- Number/rate of exacerbations (and differentiation by severity of exacerbations, i.e. requirement of hospitalisation)
- Length of exacerbation-free status
- Antibiotics and/or corticosteroids use for respiratory indication
- Symptoms/impact: CAT score and cough visual analogue score (VAS)
- Health status (quality of life measured by change in EQ-5D-5L)
- Mortality (all cause and specific)
- Healthcare utilisation (for health economic analysis)
- Adverse events of special interest (AESI) (including cardiovascular and hearingdefined as new prescription of hearing aids, liver function test (LFT) dysfunction), serious adverse events (SAEs)
- Sputum culture results, if clinically indicated and sample via routine clinical care to local lab. Record if positive result (i.e. name of organism cultured only, not cfu/ml). If multiple sent, most recent one to trial visit should be used.
- Adherence to trial medication.

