8.7 Trial medication stopping rule/early discontinuation of trial treatment

Given the nature of the discontinuation interventions assessed in this trial, a trial treatment (IMP) stopping threshold has been set following discussion with patients and respiratory specialists. This does not affect a participant's right to withdraw from the trial at any time but has been established to gain important information on and off trial treatments for secondary outcomes analyses. The aim of this rule is to balance gaining important information about intervention effects of this trial (acute and long-term perspective of the discontinuations by secondary outcomes), versus the concern of leaving a patient who may have benefited from azithromycin, being on trial medication which may be placebo.

The trial medication stopping rule: participants will stop taking trial medication (IMP) if they have 3 or more exacerbations/year. They will stop IMP as soon as practically possible and can restart their regular azithromycin prescription if advised to by their clinical team.

This trial medication stopping rule does **not** affect the trial's primary endpoint. It is also noted that there is equipoise regarding azithromycin's effect on severe (hospitalised) exacerbations.⁵ In the COLUMBUS trial, which included a COPD population cohort similar to that recommended to consider azithromycin prevention treatment for in NICE guidelines, azithromycin reduced exacerbations from a baseline 4/year to 1.94 /year (95% confidence interval (CI) 1.50-2.52) vs placebo: 3.22/year (2.62-3.97).⁴³ Thus, three or more exacerbations/year seems a reasonable IMP stopping threshold, given the upper CI of exacerbation rates with azithromycin treatment and on discussion of this element of the protocol, was considered an acceptable threshold.

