11.1.7 Participant Reporting Duration

The Sponsor expects that adverse events are recorded from the point of Informed Consent regardless of whether a participant has yet received a medicinal product to end of active trial follow-up in the trial.

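### Section 11.1.4.1 ends safety recording 28 days after trial medication stops, contradicting the protocol's own outcome window and tying ascertainment to a post-randomisation outcome

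*Protocol*

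**What the plan says.** Section 11.1.4.1 sets three windows for SAEs:

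- For participants still on medication, reporting runs from consent "until the end of trial, if a participant remains on trial medication".
- Those who stop medication "will have SAEs reported from the time the participant consents to join the trial until 28 days after ceasing trial medication".
- Those who never start are covered for 28 days from consent.

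It then adds: "All adverse events and adverse reactions will be recorded for the same period of time described above".

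Four other sections read differently:

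- Section 7.8.2 lists AESIs and SAEs among the secondary outcomes and opens with "Data pertaining to secondary outcomes will be collected over the entire trial follow-up (i.e. inclusive of time on IMP and if needed off IMP".
- Section 7.7.2 says the secondary objectives, of which adverse events is item 5, are assessed over the whole of follow-up, including time off trial medication.
- Section 11.1.7 has adverse events recorded from consent "regardless of whether a participant has yet received a medicinal product to end of active trial follow-up in the trial", with no condition on medication status.
- Section 10.5.4 lists AE and SAE assessment at every follow-up without condition. The compliance item beside it applies only to participants still on medication.

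Section 11.3 has AESIs recorded separately from other AEs but gives them no window of their own. Section 8.7 sets the stopping rule: "participants will stop taking trial medication (IMP) if they have 3 or more exacerbations/year". Such participants may then resume their regular azithromycin. Section 8.6 asks those who stop trial treatment to stay in scheduled follow-up.

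**The concern.** There are two problems. First, about 135 sites are given instructions that cannot both be followed for a named secondary outcome. Events that were never recorded cannot be recovered at analysis, so this is not a detail that a SAP can settle.

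Second, the 28-day limit is not neutral between arms. It is triggered by stopping medication, and the protocol's main stopping trigger is repeated exacerbation, which is what discontinuation may change. If discontinuation raises exacerbations, that arm is watched for less time, and the participants lost from view are its frequent exacerbators. Discontinuation could then appear safer partly because less of its follow-up was observed. Section 6 describes longer-term data on hearing loss and cardiovascular risk as urgently needed, so these outcomes matter to the trial's purpose.

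**Working it through.** **Design figure.** The event target reproduces. With a margin of 1.25, one-sided 2.7%, 90% power and 1:1 within each comparison, events = 4 × (1.927 + 1.282)² / (ln 1.25)² ≈ 827. That is 414 per arm, and 3 × 414 = 1242, as in section 15.3. The alternative behind this figure is a true hazard ratio of 1.0, so equal arms must be one of the scenarios.

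**Inputs from the protocol.**
- Exacerbation rates cited in section 8.7 to justify the stopping rule: 1.94/year on azithromycin (CI 1.50 to 2.52) and 3.22/year on placebo (2.62 to 3.97).
- Control median time to first exacerbation, section 15.3: 150 days. As an exponential rate, ln 2 / (150/365.25) = 1.69/year. At the margin, 1.25 × 1.69 = 2.11/year.
- Median follow-up of 24 months, at least 14 days between exacerbations (section 10.4.1), and the 28-day tail.

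**Assumptions, not in the protocol.** Follow-up is fixed at 24 months. The first-event hazard is used as a recurrent rate. Variation between participants is either absent (Poisson) or gamma with dispersion 1.0. Safety events occur at a constant rate that is equal between arms.

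**Step 1: chance of three or more exacerbations in 12 months.** For Poisson, P = 1 − e^(−m)(1 + m + m²/2).
- m = 1.94: 1 − 0.1437 × 4.822 = 0.307.
- m = 3.22: 1 − 0.0400 × 9.404 = 0.624.

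**Step 2: share of follow-up inside the safety window.** By simulation, medication stops at the third exacerbation within any 12 months and observation ends 28 days later. The count ratio (complete discontinuation / continued) is the ratio of these shares.

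| Scenario (continued vs complete discontinuation) | P(3 or more in a year) | Share of follow-up observed | Count ratio |
|---|---|---|---|
| Cited rates, Poisson | 30.7% vs 62.4% | 76% vs 55% | 0.72 |
| Cited rates, dispersion 1.0 | 28.7% vs 44.4% | 79% vs 67% | 0.85 |
| Design rate, HR 1.25, Poisson | 24.0% vs 35.3% | 81% vs 73% | 0.90 |
| Design rate, HR 1.25, dispersion 1.0 | 24.8% vs 31.2% | 81% vs 77% | 0.94 |
| Design rate, HR 1.0 | equal | 81% vs 81% | 1.00 |

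Counting by trial year instead of a rolling year moves the ratios only slightly, to 0.73 and 0.86 at the cited rates and 0.92 and 0.95 at HR 1.25. Spreading follow-up over 9.5 to 38.5 months gives 0.89 to 0.94 at HR 1.25. The cited rates are themselves imprecise: at the nearest ends of their intervals (2.52 vs 2.62) the step 1 probabilities are 46.1% and 48.7%.

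**Step 3: loss with equal arms.** At HR 1.0 the observed share is 81 to 82% with a rolling year and 84 to 86% by trial year. Some 14 to 19% of follow-up is therefore unobserved in every arm.

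**Step 4: does person-time solve it?** If safety risk is unrelated to exacerbation proneness, dividing by observed time removes the deficit. Suppose instead that each participant's safety risk is proportional to their exacerbation proneness (dispersion 1.0, cited rates). The captured share of events is then 57.8% vs 43.2%, on observed time of 78.6% vs 67.1%. The apparent rate ratio is (0.432/0.671) / (0.578/0.786) = 0.644/0.735 = 0.88 when the truth is 1.00. At HR 1.25 it is (0.545/0.767) / (0.615/0.813) = 0.94.

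**The case against.** A reader might infer that the rule will stop far more participants in the discontinuation arms and that the safety comparison is therefore biased towards discontinuation. The protocol does not support that as a statement of fact. The 1.94 and 3.22 rates come from a placebo-controlled trial with a baseline of 4 exacerbations a year. This trial enrols people already on azithromycin for at least 3 months and free of exacerbation for at least 6 weeks. At the protocol's own design rate the differential is modest at the margin and absent if the arms are equal. No rate is given for the seasonal arm, so nothing can be calculated for it. All of this stands, and it makes the bias conditional.

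A reader might also infer that the cardiovascular and hearing questions could not be answered by randomised comparison. That goes too far. Section 13.1.2 reports all deaths and collates cardiovascular mortality. Sections 10.5 and 10.7 obtain admissions and deaths by record linkage, where available, and hospitalised infarction or stroke could be found there. Exacerbation and pneumonia events continue as trial outcomes. Section 10.5.4, read alone, would keep AE assessment going. The AESI cut-off is itself an inference: it follows only because AESIs are AEs or SAEs.

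Finally, nothing in the protocol commits to comparing raw counts, and an on-medication window has a rationale because participants may resume open azithromycin after stopping. Person-time would remove the simple count deficit. It would not remove the selective loss of frequent exacerbators (step 4), and an on-medication analysis does not require recording to stop. Section 15.1.1 restricts evaluation to time on medication only for subgroup analyses, so it does not resolve the conflict for the main secondary outcome.

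**Conclusion.** The contradiction is certain: section 11.1.4.1 cannot be reconciled with 7.7.2, 7.8.2, 10.5.4 and 11.1.7 as written. Following 11.1.4.1 makes safety ascertainment depend on a post-randomisation outcome.

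The size of any distortion is conditional on discontinuation raising exacerbations. Under equal true risk and constant event rates, the apparent count ratio for complete discontinuation is about 0.72 to 0.86 at the cited rates, 0.89 to 0.95 at the design rate with HR 1.25, and 1.00 at HR 1.0. The dispersion and the spread of follow-up are assumptions. Even with equal arms, up to about a fifth of follow-up goes unobserved. The exposed outcomes are mainly arrhythmia, hearing and liver-function events that do not lead to admission, together with other AEs and SAEs. Mortality and linked admissions are not cut off.

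**What to change.** Reword section 11.1.4.1 to agree with 7.8.2 and 11.1.7. SAEs and AESIs should be recorded from consent to the end of trial follow-up for every randomised participant who remains in follow-up, whatever their medication status, including those who never start. State the AESI window explicitly in section 11.3. Compare SAEs and AESIs by randomised arm over that period, with an on-medication (plus 28 days) analysis as supplementary.

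The cost is a protocol amendment and more SAE and AESI forms after medication stops. The scheduled contacts that already ask about adverse events are in place. The stopping rule, event target and sample size do not change. For participants who stay in follow-up, coverage becomes complete in every arm, and the count ratio under equal true risk returns to 1.00.

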11.4.2 Assessment of causality

Definitely: A causal relationship is clinically/biologically certain. This is therefore an Adverse Reaction

- Probable: A causal relationship is clinically / biologically highly plausible and there is a plausible time sequence between onset of the AE and administration of the investigational medicinal product and there is a reasonable response on withdrawal. **This is therefore an Adverse Reaction.**
- Possible: A causal relationship is clinically / biologically plausible and there is a plausible

time sequence between onset of the AE and administration of the investigational medicinal product. **This is therefore an Adverse Reaction.**

Unlikely: A causal relation is improbable and another documented cause of the AE is most plausible. **This is therefore an Adverse Event.**

Unrelated: A causal relationship can be definitely excluded and another documented cause of the AE is most plausible. **This is therefore an Adverse Event.**

Unlikely and Unrelated causalities are considered NOT to be trial drug related. Definitely, Probable and Possible causalities are considered to be trial drug related.

A pre-existing condition must not be recorded as an AE or reported as an SAE unless the condition worsens during the trial and meets the criteria for reporting or recording in the appropriate section of the CRF.

11.4.3 Clinical assessment of severity

- Mild: The participant is aware of the event or symptom, but the event or symptom is easily tolerated
- Moderate: The participant experiences sufficient discomfort to interfere with or reduce his or her usual level of activity
- Severe: Significant impairment of functioning; the participant is unable to carry out usual activities and / or the participant's life is at risk from the event.

11.4.4 Recording of adverse events

Adverse events and adverse reactions should be recorded in the medical notes and the appropriate section of the CRF and/or AE/AR log. Serious Adverse Events and Serious Adverse Reactions should be reported to The Sponsor as detailed in section 11.5.

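### Serious complications of planned or elective admissions count as SAEs only if the trial medication may have caused them, a test that fits a discontinuation trial poorly

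*Protocol*

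**What the plan says.** Section 11.1.1 defines an adverse event as an untoward occurrence "which does not necessarily have a causal relationship with this treatment". Section 11.1.4 defines an SAE by seriousness alone; one criterion is that the event "requires hospitalisation or prolongation of existing inpatient hospitalisation".

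Section 11.1.4.1 then sets operational rules for this trial. It names two kinds of admission that are not SAEs: "Hospitalisations for treatment planned prior to randomisation and hospitalisation for elective treatment of a pre-existing condition will" not be treated as such. The next rule covers complications: "Complications occurring during such hospitalisation will also not be considered, recorded or reported as an SAE unless there is a possibility". The possibility meant is causation by the trial medication, which the rule explains as a potential adverse reaction.

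Section 7.8.2 lists SAEs and adverse events of special interest (AESIs) among the secondary outcomes. Section 7.7.2 makes comparison of the discontinuation strategies with continued azithromycin the purpose of the secondary objectives.

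**The concern.** Exempting an admission that was already planned is sensible, because it is not an untoward event. The complications rule goes further. It lets an investigator's causality opinion decide whether a serious event enters the SAE data, and it frames that opinion around the product taken.

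In most placebo-controlled trials the harm of interest comes from the product. In this one, two of the three arms have azithromycin withdrawn, either throughout or from April to September, and the safety question is partly whether its absence does harm. A test that asks only whether the tablet could be responsible suits one direction of harm better than the other. If the events it removes are those more likely after withdrawal, the SAE comparison would make discontinuation look somewhat safer than it is.

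**Working it through.** No figure in the protocol bears on this, so the check compares the text of its sections.

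1. **Scope of the general definition.** Section 11.1.4 has no causality condition. A complication of a hospital stay will often be serious because it prolongs that stay. Section 11.1.4 therefore includes it, and 11.1.4.1 removes it unless the causality condition is met.

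2. **What the condition asks.** The rule equates causation by the trial medication with a possible adverse reaction. Section 11.1.2 defines an adverse reaction as "All untoward and unintended responses to an investigational medicinal product related to any dose administered". Section 11.4.2 grades an event as possibly related if it is plausible and has a plausible "time sequence between onset of the AE and administration of the investigational medicinal product". The Reference Safety Information is taken from the azithromycin SmPC. No category covers harm from loss of prophylaxis.

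3. **How this works under blinding.** Section 8.4 blinds participants, site teams and the central team, so investigators cannot sort by arm. They can sort by type of event.
 - Events that look like azithromycin toxicity (diarrhoea, arrhythmia, liver abnormality) tend to pass in every arm, and would be expected more often where azithromycin is taken.
 - A post-operative non-respiratory infection is unlikely to be called a reaction to the tablet, so it tends to fail in every arm. If such infections rise on withdrawal, the losses fall mainly in the discontinuation arms.

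4. **What other routes recover.**
 - COPD exacerbations and pneumonia: 11.1.4.1 says they are recorded as trial outcomes, with no causality condition. Pneumonia is less secure, since 7.8.2 does not name it and the parallel exclusion in 11.3 omits it.
 - Deaths: all-cause and specific mortality is a secondary outcome.
 - AESIs (major cardiovascular events, arrhythmia, hearing, liver function): recorded separately under 11.3.
 - Linked hospital and mortality data (10.5): collected if available and analysed for admissions and deaths. A non-fatal complication within an existing stay is neither.
 - Ordinary AE recording: still applies. Sections 10.4.18 and 11.1.1 place AEs in the medical notes, and 11.4.4 adds the CRF and/or an AE log. Only SAEs are stated to go to the central team.

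5. **What is left.** Serious, non-fatal complications of planned or elective admissions that are not exacerbation, pneumonia or AESI, and that the investigator does not think the medication could have caused.

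6. **Size.** The protocol gives no rate of elective admission or of complications. To show scale only, assume that 5–15% of participants have such an admission each year and that 5–10% of these admissions bring a serious complication. Treat the median follow-up of about 24 months as two years for everyone:
 - admissions: 1311 × 2 × 0.05 = 131 to 1311 × 2 × 0.15 = 393;
 - serious complications: 131 × 0.05 ≈ 7 to 393 × 0.10 ≈ 39, or about 2 to 13 per arm.

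 This is not an estimate of the loss. It counts every assumed serious complication, before subtracting those recovered in step 4 or passed by the filter. It ignores the rule that SAE reporting ends 28 days after a participant stops trial medication. It also does not isolate complications caused by withdrawal, the only ones that could create the tilt.

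**The case against.** The strongest reply is that 11.1.4.1 is headed as operational definitions for this trial, so it narrows 11.1.4 deliberately. The trial is pragmatic, the drug is licensed and participants already take it, so lighter safety reporting is defensible. That stands: a reader might call the two sections a contradiction, but a general definition followed by a trial-specific restriction is a design choice. The objection is to how this restriction is framed.

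Three stronger readings are tempting, and the protocol does not support them.

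- *The trial drops harm from stopping azithromycin.* It does not. The main expected withdrawal harms, exacerbation and pneumonia, are to be recorded as outcomes whatever their cause, and deaths and AESIs have their own routes. Post-operative respiratory failure that forms part of an exacerbation would be captured.
- *The excluded events are not recorded and cannot be recovered.* The rule denies them status as an SAE. The exacerbation rule in the same section, by contrast, names both AEs and SAEs. AE recording survives; what is uncertain is whether it reaches the central database.
- *A withdrawal event can never pass.* Placebo is itself an investigational product under 9.1, assessors are blinded, and they need see only a possibility. Some such events could pass.

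It is also fair to say that no distortion has been shown, and that section 15.3.1 states the trial is not powered for secondary endpoints.

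**Conclusion.** The point holds in a narrow form and is minor. The causality condition is poorly matched to a trial whose experimental exposure is withdrawal, and it may leave the between-arm SAE comparison incomplete in a direction that favours discontinuation. The affected events are only those identified in step 5 of the check; central capture of these is not assured.

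The direction rests on two assumptions that the protocol cannot confirm: that blinded investigators judge causality by how closely an event resembles azithromycin toxicity, and that some complications outside the other capture routes become more frequent when azithromycin is withdrawn. The number affected cannot be estimated from the protocol and is probably small. The case for acting is that the selection rule is avoidable and cheap to remove.

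**What to change.** In section 11.1.4.1, keep the exemption for the pre-planned or elective admission itself. Delete the causality condition on complications and state instead that a complication which itself meets a seriousness criterion in 11.1.4 (for example, it prolongs the stay, is life-threatening or is fatal) is recorded as an SAE whatever its assessed cause, unless it is a COPD exacerbation or pneumonia recorded as a trial outcome.

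Causality would still be assessed, and would still determine which events are adverse reactions and need expedited reporting; it would no longer decide whether the event is counted. The cost is a change to one rule and a few more SAE forms. No treatment or visit procedure changes.
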